6.3. Adverse Event Reporting

The investigators will observe for adverse events at each session and conduct an interview at each session to determine whether an adverse event has occurred since the previous session. In addition, a follow-up phone call will be placed to each subject 2-3 days after the completion of the exercise and stimulation session to determine if any adverse events had occurred after the participant left the study.

6.3.1. **Serious Adverse Events (SAE) –**

A SAE is defined as any untoward medical occurrence, whether related to the study device or procedure or not, that meets one or more of the following criteria:

- Results in death
- Is life-threatening
 - Refers to an event in which the subject was at risk of death at the time of the event: it does not refer to an event that hypothetically might have caused death if it were more severe.
- Requires hospitalization > 24 hours
- Requires prolongation of existing hospitalization
- Results in persistent or significant disability/incapacity
- Results in fetal distress, fetal death, or congenital anomaly or birth defect

The relationship of the SAE to the study device and/or procedure will be evaluated by the investigator according to the following definitions:

- Unrelated: AE is not related to the study-specific devices or procedures
- Probably Related: AE has a strong temporal relationship to the study –specific devices or procedures, or another etiology is unlikely
- Unknown: Relationship of the study-specific devices or procedure and alternative etiology is unknown

Data for those SAEs determined to be “probably related” to the study devices or procedures, whether “expected” or “unexpected” will be collected and an emergent DSMB meeting will be held to determine if the study stopping rule criteria has been met. (section 7.4 and 7.5)

Otherwise all SAEs will be reported in summary form at the time of IRB continuing review.

6.3.2. *Unexpected Adverse Device Events (UADE)*

Any serious adverse effect on health or safety or any life-threatening problem or death caused by, or associated with, a device, if that effect, problem or death was not previously identified in nature, severity, or degree of incidence in the investigational plan or application (including a supplementary plan or application), or any other unanticipated serious problem associated with a device that relates to the rights, safety, or welfare of subjects.

Problems/events that are unanticipated and involve new or increased risk to subjects should be reported to the IRB within 5 working days if, in the opinion of the PI, they are possibly, probably or definitely related to the research procedures.

Those serious, unanticipated problems/events that the PI deems unlikely or not related and do NOT meet the IRB’s definition of UPIRTSO and should be reported in summary form at the time of IRB continuing review.

6.3.3. *Expected Adverse Events (AE)*

Those adverse events identified as Potential Risks (section 9.2) will be collected and reported in summary form at the time of IRB continuing review Data and Safety Monitoring Board (DSMB)

The DSMB will consist of one physician, one faculty member familiar with spinal stimulation and one biostatistician. None of the Board members will be directly involved with the study. The DSMB will meet semiannually to review all reportable events. If a SAE related to the study devices or procedures occur, an emergent DSMB meeting will be held to assess whether the event meets the stopping rule criteria.

6.3.4. *Stopping Rules*

If a SAE occurs, that is deemed by the PI as being **related to the study devices or study procedure**; the study will be put on hold and reviewed by the DSMB to determine whether the study can continue.

6.4. *Protocol Deviations/Violations*

Any deviation from the investigational plan to protect the life or physical well-being of a subject in an emergency shall be reported to the IRB within 5 working days after the emergency occurred. Otherwise, deviations not meeting UPIRTSO criteria should be reported in summary form at the time of IRB continuing review.

7. Bibliography

2. **Borg GA.** Perceived exertion. *Exerc Sport Sci Rev* 2: 131-153, 1974.

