The prevalence of HTN is higher in men until after menopause in women when the prevalence of HTN surpasses that of age-matched men(23). In the world, 25% of adult women are hypertensive, and in the United States, >75% of women over 60 years of age are hypertensive (4, 21). Aging is associated with elevated sympathetic activity. As such, sympathetic activity was found to be lower in women than in men among subjects <49 yrs., but the same in men and women among those that were ≥ 50 yrs(14). Importantly, sympathetic activity is greater in postmenopausal compared with age-matched premenopausal women(14). *In summary, the prevalence of HTN is higher in older women and sympathetically mediated increases in BP may be of more importance, demonstrating the need for investigating sex differences in the exercise blood pressure response in adults with HTN.*

Exercise Pressor Reflex in HTN

HTN can be characterized by chronic elevations in sympathetic nerve activity(13) which contributes to the abnormal augmented exercise pressor reflex(19). The afferent arm of this reflex is composed of mechanically (group III) and metabolically (group IV) sensitive skeletal muscle afferents which are known to become overactive or more sensitive in HTN (7, 15). As such, the autonomic response to exercise is altered, generating exaggerated increases in BP, heart rate, and SVR. Therefore, the risk for experiencing a cardiovascular or cerebrovascular event during or immediately after exercise is greatly elevated (6, 10, 18). This circumstance is regrettable as it limits the safety of exercise as a

treatment for HTN; a treatment with demonstrated potential for lowering BP and improving cardiovascular health (3).

[figure not shown]
Current Treatments in HTN

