1.2. Study Design

This is a single center study conducted at the University of Minnesota, enrolling up to sixty subjects (30 men and 30 post-menopausal women). Subjects will be assigned to one of the two study arms, (Dynamic Exercise or Spinal Cord Stimulation) and then crossover to the other arm after the initial assignment is complete. However, if the screening MRI/CT or blood work determines the subject is not a candidate for spinal cord stimulation or if the participant decides they would like to participate in the

exercise arm of the study but not the spinal cord stimulation arm, then they will be assigned to the Dynamic Exercise arm only.

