3.1. Pre-Screening

Interested adults will be pre-screened by a study team member over the phone. Adults that are interested in the study will be invited to schedule a screening visit.

A schedule of Assessments for the study visits is provided in **Figure 1**.

Figure 1: Schedule of Assessments

Procedure	Telephone pre-screening	Screening Session	Dynamic Exercise Session	Dynamic Exercise and SCS Session
Eligibility Screening	X			
Consenting Process		X		
Activity and Health Questionnaire		X		
VO ₂ Max		X		
Women: Confirmation of Menopause ¹		X		
CBC and INR		X		
Lumbar Screening MRI or CT ²		X		
Pill count sheet to track medication		X		
Vitals (HR and BP), Height, Weight		X	X	X
ECG		X	X	X
SCS Leads Implantation				X
Radial Arterial Line Insertion				X
Exercise 30% VO ₂ Peak			X	X
Blood draws				X
Follow-up phone call to assess for adverse events (3 – 6 days post visit)				X

¹ FSH lab test required if no history of oophorectomy

² For women if no history of oophorectomy and FSH testing results are not available at the time of MRI

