3. Blood pressure will be measured continuously via noninvasive finger plethysmography.
4. Gas exchange and ventilation will be measured via automated metabolic system (Medical Graphics Co., St. Paul, MN).

[figure not shown]

Figure 3. Protocol for Dynamic Exercise Arm

3.1.1. ***Dynamic Exercise and Spinal Cord Stimulation Session***

Exercise and Stimulation Session

1. Vitals, height and weight
2. SCS lead placement
3. Radial arterial line insertion
4. Exercise 30% VO₂ Peak with Stimulation
5. Blood draws
6. Lead removal
7. Adverse Event assessment

Follow-up: A phone call to the participant will be placed 2-3 days after the study to confirm that no adverse events have taken place as a result of the study.

[figure not shown]

Figure 4. Protocol for Exercise and Spinal Cord Stimulation Session

Spinal Cord Stimulation (SCS) Trial Lead Placement

SCS leads will be temporarily placed in the lumbar/thoracic epidural space in a manner that is standard for the clinical placement of trial leads in humans. Insertion of the lumbar SCS leads and arterial catheter will be conducted by qualified anesthesiologist or neurosurgeon.

SCS lead placement will occur in a sterile environment. This is done using local anesthesia with (2%) lidocaine or a similar drug and fluoroscopy to guide lead placement. Subjects lay prone and their low back is injected with lidocaine to numb the area. Another needle is placed into the epidural space within the spinal canal. Once the needle is properly in position, the SCS leads are passed through the needle and placed in the correct position via fluoroscopy (Figure 5A). A second lead may be placed in the same manner. Once the leads are placed, they will be connected to an external trial stimulator that provides stimulation current to the implanted lead. Stimulation produces a light, often pleasant tingling sensation in the legs and back, also known as paresthesia. Once the placement is complete, the needles are removed from the back and the stimulator leads left in place and secured with transparent tape (Figure 5B). Once the experiment is complete, the leads are removed by gently pulling them out by the physician with a bandage applied to the wound site.

Arterial catheter placement

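### No adverse-event contact is scheduled after a final Dynamic Exercise session, so delayed events there surface only if reported spontaneously

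*Combined protocol and SAP*

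**What the plan says.** Adverse events are solicited in two ways.

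- **At sessions.** Section 6.3 has the investigators observe for events at each session and "conduct an interview at each session to determine whether an adverse event has occurred since the previous session".
- **By telephone.** Section 6.3 adds that "a follow-up phone call will be placed to each subject 2-3 days after the completion of the exercise and stimulation session". Its stated purpose is to learn of events arising once the participant is no longer in the study. Figure 1 (Schedule of Assessments, section 3.1) lists "Follow-up phone call to assess for adverse events (3 – 6 days post visit") with a single mark, in the Dynamic Exercise and SCS Session column. The description of that session, under section 3.1.1, says: "A phone call to the participant will be placed 2-3 days after the study to confirm that no adverse events have taken place".

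On order, section 1.2 assigns participants to one of two arms and then crosses them over, so either session can come last. The Study Summary calls the trial a randomized-order study. Section 1.3 puts the two visits about one week apart. Anyone unsuitable for stimulation, or unwilling to have it, stays in the trial: "then they will be assigned to the Dynamic Exercise arm only".

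For a serious adverse event (SAE) that the PI judges related to the devices or to a study procedure, section 6.3.4 says "the study will be put on hold and reviewed by the DSMB to determine whether the study can continue".

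**The concern.** The interview looks backward, so it cannot cover time after the last session. Only the call looks forward, and it is triggered by the stimulation session alone. For anyone whose last session is Dynamic Exercise, planned ascertainment ends at that visit.

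Two things are at stake. First, the SAE definition and the hold cover study procedures as well as the device, so a serious event related to the Dynamic Exercise session counts. One SAE criterion, a hospital stay of more than 24 hours, cannot be recognised at the visit itself and needs some later contact to be found. Second, section 6.3 says the call goes to every subject and is meant to find events after departure. As triggered, it does this only for participants who have stimulation last.

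**Working it through.** The documents give no event rate or count on this point, so there is no plan figure to reproduce. The check sets the contact rules against the possible session orders.

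**Step 1. Solicited contacts by pathway** (sections 1.2, 1.3, 3.1, 3.1.1 and 6.3)

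| Pathway | Contact after the first session | Contact after the last session |
|---|---|---|
| Dynamic Exercise, then stimulation | Interview at the stimulation visit, about a week later | Call |
| Stimulation, then Dynamic Exercise | Call, then interview at the Dynamic Exercise visit | None scheduled |
| Dynamic Exercise only | Not applicable | None scheduled |

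In the second row the call falls 2-3 or 3-6 days after stimulation, while the Dynamic Exercise visit is about 7 days after it. The call is therefore made before the participant has finished the study. In the third row there is no stimulation session to trigger a call.

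**Step 2. How many participants.** Let N be the number of participants, E the number who are exercise-only, and s the share of crossover participants who have stimulation first. Those ending on Dynamic Exercise number

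L = E + s × (N − E).

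N is 40 in the Study Summary and up to 60 in section 1.2. Neither E nor s is stated. Under assumed values:

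- N = 40, E = 0, s = 0.5: L = 0 + 0.5 × 40 = 20 (50%)
- N = 60, E = 0, s = 0.5: L = 0 + 0.5 × 60 = 30 (50%)
- N = 60, E = 20, s = 0.5: L = 20 + 0.5 × 40 = 40 (67%)
- s = 0: L = E, which may be 0
- s = 1: L = N, that is, everyone

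The value E = 20 is 60 − 40. Section 3.1.1 describes that margin as an allowance for attrition, so using it for exercise-only participants is an assumption.

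**Step 3. Chance that the gap contains at least one event.** With an assumed delayed-event rate p per participant after Dynamic Exercise, the chance of at least one among n participants is 1 − (1 − p)^n.

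| p (assumed) | n = 20 | n = 30 | n = 40 |
|---|---|---|---|
| 0.5% | 9.5% | 14.0% | 18.2% |
| 1% | 18.2% | 26.0% | 33.1% |
| 2% | 33.2% | 45.5% | 55.4% |

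For example, 1 − 0.99^20 = 0.182. These figures show scale only.

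**Step 4. The call window.** Figure 1 gives 3-6 days, while the session description and section 6.3 give 2-3 days. The windows share only day 3. This is a separate contradiction, and neither window closes the gap in Step 1.

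**The case against.** The strongest defence is that tying the call to stimulation is proportionate to risk. That session adds epidural leads and an arterial catheter, and section 6.2 lists delayed problems such as infection and a spinal headache lasting 1-5 days, which a call some days later can detect. The Dynamic Exercise session is submaximal cycling with cuffs and finger plethysmography. This justifies keeping the call after stimulation. It does not explain why participants who end on Dynamic Exercise are never asked, given the aim stated in section 6.3.

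It can also be said that stimulation was meant to come last, and that the randomization concerns only the stimulation frequencies. Section 1.2 does not fix that order. If it were fixed, the exercise-only participants would still have no call.

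Several stronger readings are tempting, and the documents do not support them.

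- *Delayed events cannot reach the stopping rule.* Section 6.3.4 applies to any SAE judged related and sets no condition on how it becomes known. A self-reported event or one learned of through hospital care still triggers the hold.
- *The Dynamic Exercise session has no adverse-event check.* Its step list names none, but section 6.3 requires observation and an interview at every session. At most a cross-reference is missing.
- *The background risk statement shows that many events would be missed.* It says that "the risk for experiencing a cardiovascular or cerebrovascular event during or immediately after exercise is greatly elevated". That is the period in-session observation largely covers, and no rate is given for later days.
- *Comparisons of adverse events between arms would be biased.* Section 5 plans no such comparison, and section 6.3 plans summary reporting.
- *Stimulation-session events are missed in participants who have stimulation first.* They are covered by the call and by the interview about a week later.

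**Conclusion.** The gap is real but narrow. Exercise-only participants, and any who have stimulation first, have no scheduled adverse-event contact after their final Dynamic Exercise session. Delayed events in that period, including SAEs that would put the trial on hold, depend on spontaneous reports. This conflicts with the purpose that section 6.3 gives for the call.

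That conclusion rests on the text alone. Its size does not: with the order split and the number of exercise-only participants unstated, the count could lie anywhere from none to all. The figure of 20 holds only for a 1:1 order among 40 crossover participants, before any exercise-only participants are added. A reader should not take 20 to 40 as an estimate, nor infer that serious events would necessarily go undetected. The change is worth making because it is cheap and closes a gap in safety ascertainment.

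**What to change.** - Keep the call after the stimulation session.
- Add a call after each participant's last session when that session is Dynamic Exercise. State expressly that this covers exercise-only and stimulation-first participants.
- Make the change in Figure 1 (a mark in the Dynamic Exercise column, with a footnote saying when it applies), in the session descriptions under section 3.1.1, and in section 6.3.
- Reconcile the call windows of 3-6 and 2-3 days so that all three places agree.

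The cost is an edit to the protocol text and one extra phone call per affected participant by existing staff. No new study procedure is needed, and the stopping rule is unchanged.

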1.3. Study Duration

The subjects will participate in two study visits that will be approximately one week apart. Subject participation in the study is up to 4 weeks. Study enrollment is anticipated to take approximately 2.5 years.

2. Study Population

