6.2. Potential Risks

- Maximal Exercise Testing Protocol: A graded exercise protocol will be used on an upright cycle ergometer to volitional fatigue. The protocol will be discontinued immediately if any one of the following occur:

- 1) subject desire to stop,
- 2) drop in systolic blood pressure > 10 mmHg with increasing workload when accompanied with evidence of ischemia,
- 3) severe angina,
- 4) sustained ventricular tachycardia,
- 5) ST segment elevation > 1.0 mm in leads without diagnostic Q waves,
- 6) technical difficulties in monitoring ECG or systolic blood pressure or
- 7) completion of data collection.

The protocol will also be discontinued if any two of the following occur:

- 1) failure of heart rate to increase with increasing workload,
- 2) plateau in VO₂,
- 3) RER > 1.10,
- 4) perceived exertion > 18 (Borg 6-20 point scale),
- 5) systolic blood pressure > 250 mmHg, and 6) increased nervous system symptoms (e.g. ataxia, dizziness or syncope).

Risks of maximal exercise include: leg pain and fatigue, shortness of breath and general exhaustion.

- Spinal Cord Stimulator Placement: Placement of spinal leads will occur under local anesthesia (2% lidocaine). Therefore, minimal pain will be felt with electrode placement. There may be bruising or bleeding at the needle puncture site. There is a risk for infection at the insertion site which is extremely rare in healthy patients. Soreness at the needle site may occur once the local wears off. This is typically very minor and either requires no treatment or simple over-the-counter treatments. On an extremely rare occasion, nerve root/spinal cord trauma with the placement may occur that may lead to paralysis.
 - There is also a less than 1% risk of dural puncture and a "spinal headache." Spinal headaches may be present for 1-5 days and usually resolve with conservative therapy (rest, fluids, and analgesics such as ibuprofen or acetaminophen). A procedure known as a "blood patch" may be needed where the subject's own blood will be injected using similar techniques as the placement of the leads. This procedure is safe and very effective in treating spinal headaches. This risk is lower when the procedure is performed by a highly experienced individual.

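### For participants stimulated last, the only adverse-event call can fall before the protocol's 1-5 day spinal-headache period ends, depending on which of two conflicting call windows applies

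*Combined protocol and SAP*

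**What the plan says.** **The call.** Section 6.3 (Adverse Event Reporting) states that "a follow-up phone call will be placed to each subject 2-3 days after the completion of the exercise and stimulation session". The description of the Dynamic Exercise and Spinal Cord Stimulation Session in section 3 gives the same timing: "A phone call to the participant will be placed 2-3 days after the study to confirm that no adverse events have taken place". The Schedule of Assessments (section 3.1, Figure 1) lists the call under the stimulation session only, with a different window: "Follow-up phone call to assess for adverse events (3 – 6 days post visit".

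**The other contacts.** Section 6.3 also has the investigators "conduct an interview at each session to determine whether an adverse event has occurred since the previous session". Under section 1.2, participants start in one arm and cross over to the other, and section 1.3 says "The subjects will participate in two study visits that will be approximately one week apart".

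**The harm.** Section 6.2 (Potential Risks, Spinal Cord Stimulator Placement) puts the risk of dural puncture with spinal headache below 1%. It adds that "Spinal headaches may be present for 1-5 days and usually resolve with conservative therapy" and that "A procedure known as a 'blood patch' may be needed where the subject's own blood will be injected", by a technique similar to lead placement.

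**Reporting.** Under section 6.3.3, expected adverse events are collected and summarised for the IRB at continuing review, and the DSMB meets twice a year on reportable events. No section requires an ongoing event to be followed until it resolves.

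**The concern.** Lead placement is the most invasive procedure in the study, and spinal headache is a named risk of it, with a stated time course. The plan's last scheduled safety contact should reach the end of that time course. Whether it does depends on session order and on which call window applies.

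A participant stimulated first is interviewed at the exercise session about a week later, which covers the whole period. A participant stimulated last has only the call. If the call comes while a headache is still present, nothing in the plan obtains its end date, shows whether a blood patch followed, or records the outcome.

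The safety summary for the IRB and DSMB would then be incomplete for a known procedural harm, and follow-up would differ by session order. Section 1.1 says the pilot data are meant to justify larger trials, so its record of procedural harm is one of its useful outputs.

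**Working it through.** The plan gives no figure of its own for this point, so there is none to reproduce. The check compares days and then gives a sense of scale.

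**Inputs**
- Call window: 2-3 days (section 6.3 and the stimulation-session description) or 3-6 days (Schedule of Assessments).
- Headache period: 1-5 days (section 6.2).
- Dural puncture risk: below 1% (section 6.2). The ceiling p = 0.01 is used, with 0.005 as an assumed lower value.
- Participants: 20 women and 20 men per arm (section 3.1.1, Screening and Baseline), so 40 stimulated.
- Assumptions: onset on the procedure day; for the smaller group, an even split of session order, so 40 / 2 = 20 stimulated last.

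**Step 1: days left uncovered.** Days uncovered = 5 - day of call.

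| Day of call | Within 2-3 day window | Within 3-6 day window | Days uncovered |
|---|---|---|---|
| 2 | yes | no | 3 |
| 3 | yes | yes | 2 |
| 4 | no | yes | 1 |
| 5 | no | yes | 0 |
| 6 | no | yes | -1 (period has ended) |

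The whole of the 2-3 day window falls short. In the 3-6 day window, days 3 and 4 fall short and days 5 and 6 do not. Day 3 is the only day that satisfies both windows, and it leaves 2 days uncovered. Removing the contradiction by adopting 2-3 days, or the shared day 3, would therefore leave this gap open.

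**Step 2: who is affected.** Participants stimulated first have the call and then an interview at about day 7, which is after day 5. Participants stimulated last have the call alone.

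**Step 3: scale.** Expected dural punctures = n × p. Chance of at least one = 1 - (1 - p)^n.

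| Stimulated last | p | Expected | Chance of at least one |
|---|---|---|---|
| 20 (even split) | 0.01 | 0.2 | 1 - 0.99^20 = 18.2% |
| 20 (even split) | 0.005 | 0.1 | 1 - 0.995^20 = 9.5% |
| 40 (all) | 0.01 | 0.4 | 1 - 0.99^40 = 33.1% |
| 40 (all) | 0.005 | 0.2 | 1 - 0.995^40 = 18.2% |

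The rows at p = 0.01 are upper bounds, because the protocol says the risk is below 1%. All rows count any dural puncture. The relevant event is a headache that outlasts the call, which is a fraction of these that the documents do not give.

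**The case against.** The strongest reply is that the real defect is the contradiction between the two call windows. If the Schedule of Assessments governs and calls are made on day 5 or 6, there is no gap. That is correct, and a reader who takes day 2-3 as the protocol's only timing would overstate the point. What stands is that other ways of resolving the contradiction leave the gap open, so the reconciled window has to be checked against section 6.2 as well.

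Three further objections limit the point.

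- **Duration is not onset.** The 1-5 days describe how long a headache may be present, not when it begins. With onset on the procedure day, the headache already exists at the call and would be detected. A reader might infer that headaches would be missed altogether; the documents do not support that. A later onset would move the end of the period later. The documents give no time course for insertion-site problems, so the gap cannot be sized for them.
- **The call is not a stated cut-off.** Section 6.3.3 sets no end date for collecting expected events. Nothing says that staff drop a headache reported at the call or ignore a later report. Consent and contact pages are not in the public document, so instructions to participants on reporting problems cannot be presumed absent. The gap is in scheduled contact and in the lack of a follow-to-resolution rule.
- **The stopping rule has a higher threshold.** A reader might infer that late headaches or blood patches would escape the stopping rule. That rule and the emergent DSMB meeting need a related serious adverse event. A headache or blood patch counts only if it meets a listed criterion, such as hospitalization for more than 24 hours.

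**Conclusion.** The point holds in limited form. For participants whose stimulation session is last, a call on days 2-4 precedes the end of the protocol's own headache period by 3 to 1 days; a call on days 5-6 does not. What can go unrecorded is duration, later treatment (including a blood patch) and outcome, not the occurrence of a headache present at the call. The result is a possibly incomplete IRB and DSMB safety summary and follow-up that depends on session order.

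The expected number of cases is small. At the 1% ceiling the chance of at least one dural puncture is at most 18% among 20 participants stimulated last. The 33% figure is not the general size of the problem: it applies only if all 40 are stimulated last. Both overstate the chance of a headache that outlasts the call. The conclusion assumes onset on the procedure day, and the 18% also assumes an even split of session order. The case for a change rests on complete follow-up at very low cost, not on a high event rate.

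**What to change.** Reconcile the Schedule of Assessments, the stimulation-session description and section 6.3 with one another and with the 1-5 day figure in section 6.2. For participants stimulated last, the last scheduled adverse-event contact should not precede the end of that period. Either the timing of the existing call or one further brief call by the same staff would achieve this.

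At that contact, record whether a headache or insertion-site problem occurred, its start and end dates, any treatment (including a blood patch) and the outcome. Ask the same questions at the interview already planned for participants who return for the exercise session, so that ascertainment does not depend on session order.

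The cost is protocol wording and, if a call is added, one short call for about 20 participants under an even split, or up to 40. Section 1.3 allows up to 4 weeks of participation, so there is room for it. If the existing call is moved instead, the drawback is a later first contact after the procedure.

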1.1. Background and Significance

Health Issue Addressed

Hypertension (HTN) is a silent, invisible killer that rarely causes symptoms and is one of the key causes for cardiovascular disease (CVD). Sympathetically mediated cardiovascular responses to exercise (over activation of group III/IV skeletal muscle afferents, sympathoexcitation) are exaggerated in adults with HTN (10). These abnormally large changes in hemodynamics during exercise (exercise-induced HTN) increase the risk for adverse cardiovascular or cerebrovascular events during or immediately following a bout of exercise (6, 18, 23). Importantly, HTN used to be considered a man's disease, however, women following menopause, are now at a greater risk for CVD compared with men (23). Despite the greater increase of HTN in postmenopausal women, the sex difference in the exercise pressor response (EPR) in adults with HTN is unclear. Further, treatment guidelines for HTN management remain inconsistent, particularly for young and aged women (23). Therefore, there is a critical need to understand if the EPR is differentially regulated in postmenopausal women with HTN and to determine an effective early intervention that can target exercise-induced hypertension in these women.

Gap in Knowledge Addressed

Generally, suggested non-pharmacological methods utilized to treat HTN usually include change in diet and exercise, but unfortunately, exercise is risky for HTN patients that experience exaggerated sympathoexcitation in response to exercise (6, 10, 18). So, there is a large gap in knowledge in regards to the best non-pharmacological method for reducing BP in HTN patients. As such, we propose a novel treatment that is in current use for pain disorders(12), but may serve as a promising treatment for HTN. Spinal cord stimulation (SCS) works by modulating afferent input at the dorsal column of the spinal cord and causes vasodilation in the peripheral blood vessels (5). Therefore, the use of SCS can be an innovative technique to reduce systemic effects of sympathoexcitatory afferent feedback from the active skeletal muscle, and thereby increase peripheral vasodilation and reduce blood pressure (BP) in adults with HTN. This will be a pilot study and the generated data will justify conducting larger clinical trials.

Sex Differences in HTN

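### A related event whose only serious feature is an admission of 24 hours or less, or an intervention to prevent permanent impairment, triggers neither the study hold nor the emergent DSMB meeting

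*Combined protocol and SAP*

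**What the plan says.** Section 6.3.1 defines an SAE as an untoward medical occurrence "that meets one or more of the following criteria". The list has six entries: death; a life-threatening event; "Requires hospitalization > 24 hours"; "Requires prolongation of existing hospitalization"; "Results in persistent or significant disability/incapacity"; and a fetal or congenital outcome. The life-threatening entry carries a note: "Refers to an event in which the subject was at risk of death at the time of the event". It excludes events that might have been fatal had they been worse.

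For SAEs judged probably related, 6.3.1 says that "an emergent DSMB meeting will be held to determine if the study stopping rule criteria has been met". The DSMB paragraph that follows 6.3.3 repeats this for related SAEs. Under 6.3.4, when the PI deems an SAE related to the device or procedure, "the study will be put on hold and reviewed by the DSMB to determine whether the study can continue".

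Three other routes exist. Under 6.3.2, unanticipated problems with new or increased risk go to the IRB within 5 working days if the PI thinks them at least possibly related. Under 6.3.3, events already listed as potential risks are summarised at IRB continuing review. The DSMB also meets twice a year to look at reportable events.

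**The concern.** The list treats two kinds of hospital stay unevenly. Any lengthening of an existing stay counts, but a new admission counts only above 24 hours, and the protocol gives no reason for the difference. Participants attend as outpatients for sessions lasting hours, so a new admission is the relevant case and prolongation hardly ever is.

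The Background (1.1) says that exaggerated haemodynamic responses in hypertension "increase the risk for adverse cardiovascular or cerebrovascular events during or immediately following a bout of exercise". Section 6.2 adds the risks of lead placement, the arterial line and sedation, and concedes that less is known about stimulation during exercise. A related complication that is admitted, settles and goes home within a day could be just the signal the DSMB would want before the next lead placement. Under the rule as written it need not prompt a pause or an urgent meeting.

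**Working it through.** The plan states no figure on this point, so the check is a trace from the definition to the safeguards.

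**1. Which SAE criteria can apply here.** The fetal entry has almost no application in men and postmenopausal women. The prolongation entry needs someone already in hospital, whereas 6.2 describes ambulatory subjects catheterised for a few hours. For a related event that is not fatal, life-threatening or disabling, the admission criterion is in practice the only one left, and it stops at 24 hours.

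**2. What each kind of related event sets off.**

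| Related event | SAE under 6.3.1? | Emergent meeting and hold? |
|---|---|---|
| Death | Yes | Yes |
| At risk of death at the time, home within 24 hours | Yes | Yes |
| Persistent or significant disability, no admission | Yes | Yes |
| Admission over 24 hours, no other criterion met | Yes | Yes |
| Admission of 24 hours or less, no other criterion met | No | No |
| Intervention that prevents permanent impairment, no admission over 24 hours, no other criterion met | No | No |

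The last two rows are the gap.

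**3. Whether another route closes it.** The 5-working-day report goes to the IRB and has no hold or DSMB meeting attached. It also applies only if the event is unanticipated and brings new or increased risk. An event of a kind listed in 6.2 goes to summary reporting. The semiannual DSMB review covers reportable events, a term the protocol does not define. None of these is an immediate safeguard.

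**4. How much exposure could pass between routine DSMB meetings.** This assumes even accrual and one stimulation session per participant. Inputs are 40 participants per arm (20 women and 20 men) and 60 enrolled (3.1.1, Screening and Baseline), about 2.5 years of enrolment (1.3), and a two-year study duration (Study Summary). Sessions per interval = participants ÷ number of half-years.

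- 2.5 years: 2.5 ÷ 0.5 = 5 intervals; 40 ÷ 5 = 8 and 60 ÷ 5 = 12.
- Two years: 2 ÷ 0.5 = 4 intervals; 40 ÷ 4 = 10 and 60 ÷ 4 = 15.

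The range is 8 to 15 sessions. The upper end supposes that all 60 enrolled reach the stimulation session, which 1.2 does not expect, since some may take the exercise arm only. These are counts of sessions, not of events.

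**The case against.** The strongest reply is that a 24-hour threshold is a stated choice that contradicts nothing else in the protocol, and that the gravest events are caught without it. The second half is right. A reader might infer from the admission line that any short-stay event, however grave, escapes the safeguards. The documents do not support that: the criteria are alternatives, so a life-threatening or disabling event is an SAE even if the participant goes home the same day.

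A reader might also infer that sub-SAE events go unreviewed. That is too strong as well, given the IRB report and the semiannual review. What stands is that neither is a hold or an urgent DSMB meeting.

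It is tempting to size the gap with the dural-puncture risk of less than 1% in 6.2 and to use a blood patch as the example. The documents do not support this either. They give no rate for patches, and they describe spinal headache as usually resolving with conservative care. An outpatient patch for such a headache would not clearly count as preventing permanent impairment, so the amended definition might not capture it.

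Finally, the Background statement on exercise events concerns people with hypertension in general, and the protocol does not call it the main hazard of this trial. It shows that short-lived acute events are plausible, not that they are frequent.

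**Conclusion.** The point holds in a limited form. A related event whose only serious feature is an admission of 24 hours or less, or an intervention to prevent permanent impairment without a longer admission, falls outside 6.3.1 and so triggers neither the emergent DSMB meeting nor the hold. This follows from the text and rests on no numerical assumption. How often it would matter is unknown, because the protocol gives no frequency for short admissions. The 8 to 15 sessions between routine meetings rest on even accrual and show only the exposure that could build up. This is a cheap improvement to a reporting definition, worth making because the procedure is invasive, new in this setting and done in outpatients. It is not a failure of the safety plan as a whole.

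**What to change.** Amend the SAE definition in 6.3.1 in three places:

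- Delete the 24-hour limit, so that any unplanned hospital admission counts.
- State whether an overnight observation stay is an admission; otherwise the same ambiguity returns under another name.
- Add a criterion for an event that *requires medical or surgical intervention to prevent permanent impairment*.

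Then read 6.3.1 against the risks listed in 6.2 and reconcile the two, so that it is clear which listed risks would count as SAEs when they occur. Leave the hold and the DSMB steps as they are. The cost is a short protocol amendment and an occasional extra ad hoc DSMB review. No visit, measurement or analysis changes.
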